1.2 Trial objectives

The primary objective of Stage 2 of the STREAM trial is:

To assess whether the proportion of participants with a favourable efficacy outcome on Regimen C, the fully oral regimen, is non-inferior to that on Regimen B at Week 76, using a 10% margin of non-inferiority

The secondary objectives of the Stage 2 comparison of the STREAM trial are:

- 1. To assess whether Regimen C is non-inferior to Regimen B with regards to the proportion of participants with a favourable efficacy outcome at Week 132
- 2. To assess whether Regimen C is superior to Regimen B with regards to the proportion of participants with a favourable efficacy outcome at Week 76 and Week 132 (if non-inferiority is demonstrated at either time-point)
- 3. To compare the efficacy of 40 weeks of bedaquiline in combination with the other drugs of Regimen C with Regimen B during treatment and follow-up
- 4. To compare the efficacy of 28 weeks of bedaquiline in combination with the other drugs of Regimen D with Regimen B during treatment and follow-up
- 5. To estimate the difference between Regimen C and Regimen B_{mox} in the proportion of participants with a favourable efficacy outcome at Week 76 and Week 132
- 6. To estimate the difference between Regimen C and Regimen B_{lev} in the proportion of participants with a favourable efficacy outcome at Week 76 and Week 132
- 7. To estimate the difference between Regimen D and Regimen B in the proportion of participants with a favourable efficacy outcome at Week 76 and Week 132
- 8. To estimate the difference between Regimen B and Regimen A in the proportion of participants with a favourable efficacy outcome at Week 132
- 9. To estimate the difference between Regimen C and Regimen A in the proportion of participants with a favourable efficacy outcome at Week 132
- 10. To estimate the difference between Regimen D and Regimen A in the proportion of participants with a favourable efficacy outcome at Week 132
- 11. To investigate the safety, including the effect on mortality and tolerability of 40 weeks of bedaquiline in combination with the other drugs of Regimen C compared to Regimen B during treatment and follow-up
- 12. To investigate the safety, including the effect on mortality and tolerability of 28 weeks of bedaquiline in combination with the other drugs of Regimen D compared to Regimen B during treatment and follow-up

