1.4 Study interventions

In Stage 2 of the STREAM trial, the primary comparison being made is between Regimen C and Regimen B, with secondary comparisons between Regimen D and Regimen B. In addition, a limited number of secondary analyses will make comparisons between Regimen A and the other regimens.

Regimen A: The locally-used MDR-TB regimen in accordance with 2011 WHO MDR-TB treatment guidelines¹.

Regimen B: Regimen B forms the control regimen for the primary and secondary comparisons, and is based on the regimen described by Van Deun 2010^2 (updated results³) consisting at the start of STREAM of clofazimine, ethambutol, moxifloxacin, and pyrazinamide given for 40 weeks, supplemented by isoniazid, kanamycin, and prothionamide for the first 16 weeks; this combination is referred to as Regimen B_{mox}. With Version 8.0 of the protocol Regimen B is modified by replacement of moxifloxacin with levofloxacin (referred to as Regimen B_{lev}). Regimen B without specification of which fluoroguinolone is in the regimen

refers to either (B_{mox} or B_{lev}). With Version 10.0 of the protocol, Regimen B is further modified to replace kanamycin with amikacin in sites where:

- the national TB program has replaced kanamycin with amikacin in line with revised WHO guidance⁴ and
- amikacin is available for the trial.

Kanamycin will continue to be used until the transition takes place within each country programme.

Regimen C: Regimen C is an all-oral modified version of Regimen B, consisting of bedaquiline, clofazimine, ethambutol, levofloxacin, and pyrazinamide given for 40 weeks, supplemented by isoniazid, and prothionamide for the first 16 weeks.

Regimen D: Regimen D a shortened modified version of Regimen B, consisting of bedaquiline, clofazimine, levofloxacin, and pyrazinamide given for 28 weeks, supplemented by isoniazid, and kanamycin for the first 8 weeks.

All patients in Stage 2 of the study will be followed up to Week 132. The primary analysis will be based on data accrued to Week 76; the data accrued to the date when the last patient is projected to have reached Week 96 will be used for the secondary long-term efficacy analysis; all data accrued to Week 132 will be used in the long-term safety analysis.

1.5 **Treatment phases**

Regimen B, Regimen C, and Regimen D each consist of 2 phases; an intense phase followed by a continuation phase, as shown in Figure 1.

[figure not shown]

Figure 1: Regimen treatment phases

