6.1.1 Modelling technique used in analysis

For the primary efficacy analysis the difference in proportions of favourable outcome between Regimen B (B_{mox} and B_{lev} combined) and Regimen C with corresponding 95% confidence intervals and p-values will be estimated using a stratified analysis of the risk difference from each stratum using Cochran-Mantel-Haenszel weights.⁵ The analysis will be stratified by randomisation protocol and HIV status (as defined in Section 1.6).

6.1.2 Non-inferiority of Regimen C compared to Regimen B at Week 76

Non-inferiority will be shown if the upper bound of the 95% confidence interval of the difference in proportion of favourable outcomes at Week 76 between Regimens B and C is less than the 10% margin of non-inferiority; this must be shown in both the mITT and PP populations. An sensitivity analysis will be undertaken using the mPP population.

6.1.3 Superiority of Regimen C compared to Regimen B at Week 76

If non-inferiority is demonstrated, then superiority of Regimen C compared to Regimen B will be declared if the upper bound of the 95% confidence interval of the difference in proportion of favourable outcomes at Week 76 between Regimens B and C is less than zero,. For this analysis, the mITT population will be primary and the PP and mPP populations will be sensitivity analyses.

Secondary analyses will repeat the primary analysis but compare Regimen B_{lev} and Regimen C, Regimen B_{mox} and Regimen C, and Regimen B and Regimen D, restricting the population in each case to include only concurrent controls within site. For this analysis, the mITT population will be primary and the PP population will be sensitivity analyses. Comparisons of Regimen C and Regimen D were carried out at the time of the primary analysis but considered exploratory.

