- J. Requiring a 25 day delay between the last 2 negative culture results in participants classified as favourable. A participant's outcome will be unfavourable if previously classified as favourable but not meeting this definition. . .
- K. In the ITT analysis population
- L. In the safety analysis population

Analyses D to J will be repeated adjusted only for randomisation protocol.

6.5 **Bayesian analysis of non-inferiority**

An exploratory Bayesian analysis of non-inferiority provides an estimate of the probability that Regimen B has efficacy not much worse than Regimen C for different thresholds of what might be considered 'not much worse'.

Following methods described previously⁶, we will use Bayesian binomial regression to estimate the distribution of the (unadjusted) difference in the proportion of favourable outcomes between regimens B and C. Gaussian Normal priors will be placed on the intercept term (mean = 0.0 and variance = 100) and on the difference in proportion between regimens (Flat: mean = 0.0 and variance = 100, Sceptical: mean = 0.02 and variance 0.05, and Expected: mean = -0.02 and variance 0.05). The Flat prior is an uninformative prior

with very large variance centred around zero representing weak prior information, the Sceptical prior is centred around an absolute 2% increase in proportion of favourable in Regimen B with a smaller variance, and the Expected prior represents the assumptions used in the sample size calculations representing an absolute 2% increase in the proportion of favourable outcomes in regimen C. Initial values for the Markov Chain Monte Carlo algorithm came from estimates from the frequentist binomial regression model. This analysis will be on the mITT population.

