7.2.5 Pharmacokinetics/Pharmacodynamics

At a number of visits throughout the trial, a single blood sample is taken to determine the bedaquiline (BDQ) and M2 plasma concentrations. The BDQ plasma concentrations are used by a qualified vendor to estimate C_{trough} , C_{max} and AUC using empirical Bayes' estimation based on a population pharmacokinetic model. Individual ART plasma concentrations (LPV, RTV and NVP) and 4β -hydroxycholesterol/cholesterol ratio (as a measure of cytochrome P450 3A (CYP3A) activity) are also measured.

Participants randomised to Regimen C or Regimen D with PK data available, will be classified into 5 subgroups based on their HIV status and HIV drugs taken immediately before the PK blood draw:

- **HIV Neg:** HIV negative at baseline
- **HIV Pos, LPV/r**: HIV positive at baseline having received Liponavir/Ritonavir (but not Nevirapine) immediately before the PK blood draw.
- HIV Pos, NVP: HIV positive at baseline having received Nevirapine (but not Liponavir/Ritonavir) immediately before the PK blood draw.
- **HIV Pos, other ARV**: HIV positive at baseline having received ART (but not Liponavir/Ritonavir or Nevirapine) immediately before the PK blood draw.
- **HIV Pos, not taking ARV:** HIV positive at baseline but not receiving ART immediately before the PK blood draw.

Individual plasma concentrations will be listed and descriptive statistics generated at each sampling time, by treatment group and separately for the above defined subgroups.

Further details of the analyses of PK/PD will be described in the STREAM Stage 2 Extensive SAP.

7.3 **Health Economics**

In selected sites, acceptability of Regimens A, B, C and D to stakeholders will be analysed in terms of:

- Costs to the health system
- Household costs
- Patient treatment and support experiences
- Health worker experiences.

The analyses of health and household costs and patient and health worker experiences will be described in a separate document.

7.4 **Testing multiple outcomes**

We will make no adjustment to p-values or confidence intervals to allow for testing multiple secondary outcomes.

The STREAM primary outcome is a composite outcome of bacteriological failure, treatment failure for any reason (clinical, bacteriological, intolerance) and death. The primary analysis is non-inferiority of Regimen C versus Regimen B. If the 95% CI for the treatment effect

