(difference in proportion unfavourable by 76 weeks (C-B)) lies below the non-inferiority margin, then we will also test for superiority; because this is a closed test procedure there is no issue of multiplicity.

Secondary outcomes are divided in the protocol into efficacy outcomes, safety outcomes and acceptability outcomes. For safety outcomes it is appropriate to test each independently since it is important to identify any risks associated with Regimen C. The secondary efficacy outcomes are mostly components of the primary outcome or very closely related to the primary outcome (bacteriological and clinical outcomes). We will not adjust for multiple testing for these since they are correlated with the primary outcome (so standard adjustments are conservative).

We will report significance tests for differences between treatment arms for acceptability outcomes, but if we have failed to demonstrate non-inferiority of Regimen C versus Regimen B for the primary outcome, we will not use significance tests for these acceptability outcomes to conclude superiority.

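### SAP 6.5 words the Bayesian non-inferiority probability backwards: it asks whether control Regimen B is not much worse than Regimen C

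*SAP*

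**What the plan says.** SAP 6.5, headed as a Bayesian analysis of non-inferiority, opens by saying that the analysis "provides an estimate of the probability that Regimen B has efficacy not much worse than Regimen C", for a range of thresholds. It then describes a binomial regression for the unadjusted difference in favourable proportions between regimens B and C in the mITT population, with three priors on that difference:

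- Flat: mean 0, variance 100.
- Sceptical: mean 0.02, variance 0.05. In words, "the Sceptical prior is centred around an absolute 2% increase in proportion of favourable in Regimen B".
- Expected: "Expected: mean = -0.02", variance 0.05, described as matching the sample-size assumptions, with C better by 2 points.

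The rest of the SAP sets the direction as follows:

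- SAP 1.4: "Regimen B forms the control regimen for the primary and secondary comparisons".
- SAP 1.2: the primary objective is that the favourable proportion on Regimen C "is non-inferior to that on Regimen B at Week 76, using a 10% margin of non-inferiority".
- SAP 6.1.2: non-inferiority of C compared with B requires that the upper confidence bound for the "difference in proportion of favourable outcomes at Week 76 between Regimens B and C is less than the 10% margin of non-inferiority".
- SAP 7.4: "The primary analysis is non-inferiority of Regimen C versus Regimen B". The effect there is the "difference in proportion unfavourable by 76 weeks (C-B"), and its interval must lie below the margin.

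**The concern.** Non-inferiority has a direction. The new regimen is tested against the control, and the analysis asks how likely it is that the new regimen is not much worse. The opening sentence of SAP 6.5 puts the control in the place of the regimen under test.

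That sentence is the only statement in SAP 6.5 of the event whose probability will be reported, and the protocol's analysis section (11.6) describes no Bayesian analysis that could correct it. A programmer who followed it literally would produce a probability that moves the wrong way. It would approach 1 as Regimen C became inferior, and it would understate the support for C when C was better. Shown under a non-inferiority heading, such a figure would be read as support for C.

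**Working it through.** **1. Sign of the modelled difference.** SAP 2.1 plans for 80% favourable on B and 82% on C. The Expected prior is said to represent those assumptions:

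0.80 - 0.82 = -0.02, which is B - C.

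This reproduces the stated prior mean exactly. The Sceptical mean of +0.02 is described as favouring B, which agrees. A sceptical prior that favours B makes sense only if C is the regimen under test. SAP 7.4 gives the same scale, because C-B in unfavourable proportions equals (1 - pC) - (1 - pB) = pB - pC.

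**2. The two events.** Let d = pB - pC in favourable proportions and let M be the threshold.

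- As written (B not much worse than C): pB > pC - M, so P(d > -M).
- Intended (C not much worse than B): pC > pB - M, so P(d < M).

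The first rises with d and the second falls. With a symmetric posterior they are equal only when it is centred at zero.

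**3. Size of the gap.** Inputs:

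- M = 0.10, the margin in SAP 1.2.
- n = 172 per arm, the evaluable number in SAP 2.1. Recomputing it as (1.960 + 0.842)² × 0.3076 / 0.12² gives 168, and power at 172 is 81.0%, so the planning figure is reproduced closely.
- n = 200 per arm, the randomisation target. The figure of 172 allows for per-protocol exclusions, but SAP 6.5 uses mITT, which Protocol 11.4.1 expects to lose fewer patients. The range 172 to 200 is therefore shown.
- Flat prior and normal approximation, with variance (0.80 × 0.20 + 0.82 × 0.18)/n = 0.3076/n. The SD is 0.0423 (n = 172) or 0.0392 (n = 200).

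Formulas: as written = Φ((0.10 + d)/SD); intended = Φ((0.10 - d)/SD). For example, at d = -0.02 and n = 172 these are Φ(0.08/0.0423) = 0.971 and Φ(0.12/0.0423) = 0.998.

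| Observed B-C | As written, n=172 | Intended, n=172 | As written, n=200 | Intended, n=200 |
|---|---|---|---|---|
| -2 points (planning rates) | 0.971 | 0.998 | 0.979 | 0.999 |
| 0 (assumed) | 0.991 | 0.991 | 0.995 | 0.995 |
| +5 points (assumed) | >0.999 | 0.881 | >0.999 | 0.899 |
| +12 points (assumed) | >0.999 | 0.318 | >0.999 | 0.305 |

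**4. Robustness.**

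- If the variance is taken at the assumed observed rates (B held at 80%), the intended values are 0.867 (n = 172) and 0.885 (n = 200) at +5 points, and 0.335 and 0.323 at +12 points.
- Independent Beta posteriors with uniform priors and 200 per arm give, as written and intended: 0.980 and 0.999 for 160 vs 164 favourable (B vs C); >0.999 and 0.888 for 160 vs 150; >0.999 and 0.330 for 160 vs 136.
- In a separate set of scenarios at 172 per arm, using the Sceptical or Expected prior in place of the Flat one moved the probabilities by less than 0.05.

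**The case against.** The strongest reply is that this is an editorial slip whose meaning can be recovered. The section heading, the prior descriptions and SAP 6.1.2 all point to C against B, so a careful statistician would compute P(B-C < threshold) anyway. SAP 6.5 also says it follows methods described previously and cites a publication, which may define the reported event. The analysis is exploratory, unadjusted and mITT only, and it enters no decision rule. At the only planned scenario the two readings differ by less than 0.03, with the literal one lower; the large gaps need results that no document gives.

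It can also be said that the sign support is uneven. SAP 6.1.2 names regimens B and C without a subtraction order, and SAP 7.1.4 labels its Week 132 interval as C minus B.

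Much of this stands as a limit on weight. The documents do not show that the wrong quantity was programmed, and the scenarios at +5 and +12 points are illustrations. It does not rescue the sentence. A SAP fixes the output in advance, and two programmers, one following this sentence and one following SAP 6.1.2, would report different numbers. The B-C sign does not depend on SAP 6.1.2, because the prior descriptions in SAP 6.5 and the definition in SAP 7.4 establish it. Nothing in the objectives asks whether B is non-inferior to C.

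**Conclusion.** The concern holds. The sentence in SAP 6.5 that defines the Bayesian output reverses the two regimens and contradicts both the rest of the SAP and the priors in its own section. It is a wording error; the model, priors, population and posterior are not in question.

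Its size depends on the result. The effect is small near the planning rates and nil at zero difference. It is large if C does worse than B: at an assumed 12-point deficit, the literal probability exceeds 0.999 while the intended one is about 0.3. These figures assume a flat prior, a 10-point threshold, a normal approximation and 172 to 200 patients per arm. The primary non-inferiority conclusion is unaffected, so the severity is minor.

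**What to change.** Swap the two regimen letters in the opening sentence of SAP 6.5, so that Regimen C is the regimen judged not much worse and Regimen B is the reference. Add one line defining d as B minus C in favourable proportions and the output as P(d < threshold). It would help to name the 10-point margin as one of the thresholds, so that the result can be set beside the primary analysis.

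SAP 6.1.3 already refers in the past tense to work done at the time of the primary analysis, so the change should be recorded as a correction, and any existing program, table or text should be checked for direction. The cost is one sentence, one definition and that check. The existing posterior for B-C supplies the intended probability without a refit.

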7 ANALYSIS OF SECONDARY OUTCOMES

7.1 Efficacy outcomes

Secondary efficacy analyses will be carried out on i) data censored at Week 76, and ii) data from all visits occurring on or before the projected Week 96 visit of the last patient randomised i.e. approximately end of November 2021 (long-term efficacy data). A participant's scheduled last efficacy visit will be their latest scheduled trial visit on or before this date. In addition to the comparisons detailed below, analyses of the long-term efficacy data will include comparisons of Regimen C with Regimen D. Comparisons of Regimen C and Regimen D using data up to Week 76 were carried out at the time of the primary analysis but considered exploratory.

Secondary efficacy outcomes will be analysed on the mITT analysis population with the exception of the analysis of favourable outcome at Week 132 to determine the non-inferiority of Regimen C to Regimen B which will be analysed on the mITT, PP and mPP populations.

